1.3 Research Design and Methods

This pilot study is a 2-arm individually randomized controlled trial design in which outcomes of MMT patients randomized to MORE are compared to outcomes of those randomized to treatment as usual (TAU). In the pilot study (R21; N=31), we will randomize MMT patients with chronic pain to MORE (n=15) or TAU (n=16). This study phase will focus on establishing study feasibility in recruiting, retaining, and following up study participants before progressing to a larger Phase II clinical trial (R33, N=150). Participants with pain who are receiving MMT for an opioid use disorder (OUD) will be recruited from the New Brunswick Counseling Center (NBCC) and the Lennard Clinic.

A. *Describe, in order of occurrence, all research procedures being performed, when and where they are performed, and by whom (including procedures being performed to monitor subjects for safety or minimize risks).*

Participants will be recruited through flyers posted in the clinics, being approached by research assistants in the waiting room of their usual methadone clinic (New Brunswick Counseling Center or Lennard Clinic), and referral by clinic staff. The number of individuals who contact the study staff through the flyers or referral and who are approached by study staff in the clinics will be tracked. Number of individuals who refuse study participation and who consent to the study will also be tracked. If an individual is interested in study participation, a trained research assistant will lead the individual through the informed consent process in a private space.

Participants randomized to the MORE condition will participate in eight, weekly, two-hour group sessions led by a clinic or study counselor. Each session will contain 4-8 participants and take place in a private room at the New Brunswick Counseling Center (NBCC) or the Lennard Clinic. Attendance at each session and reasons for missing sessions will be recorded. Participants randomized to the control condition will continue receiving treatment as usual at the NBCC.

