MORE sessions. We will consider our ability to follow participants successful if we obtain 8-week assessments from at least 65% of participants and 16-week assessments from at least 50%. Although we are targeting a follow-up rate in both groups of at least 80% and 75% at 8 and 16 weeks, respectively, we set the benchmarks at 65% and 50% because, again, if necessary, we can adapt follow-up strategies for the next study, based on lessons learned in this study.

Preliminary outcome measures to be assessed during this pilot study will be time until opioid lapse and MMT dropout. Preliminary secondary outcomes will be: days of methadone medication use, days of opioid and other drug use, and changes in pain severity and intensity. Additional measures are described below.

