1.6 Study Variables

A. Independent Variables, Interventions, or Predictor Variables

Mindfulness Oriented Recovery Enhancement (MORE) structure (Intervention Condition). The MORE arm will participate in eight, weekly, two-hour group sessions led by a therapist. MORE sessions involve mindfulness training to prevent opioid relapse and reduce pain, cognitive reappraisal to decrease negative affect and regulate opioid craving, and savoring to augment natural reward processing and evoke positive emotion.¹ Each session begins with a mindful breathing or body scan meditation, followed by a debriefing session, in which the therapist provides reinforcement and troubleshooting to help guide successful implementation of mindfulness techniques. Following this debrief of the in-session mindfulness meditation, the therapist debriefs participants' homework practice of using mindfulness, reappraisal, and savoring skills to cope with pain and enhance well-being in everyday life. During this debrief of the homework practice, the therapist provides reinforcement and troubleshooting to help guide successful implementation of mindfulness, reappraisal, and savoring techniques. Next, new psychoeducational material is introduced according to the session topics outlined in Table 3. Sessions culminate with an experiential exercise, and close with a brief mindful breathing meditation. Participants are asked to practice 15 minutes of mindfulness/reappraisal/savoring skills each day (i.e. homework practice).

Table 3. MORE session content	
Week	Theme
1	Introduction to mindfulness, and the relationship between nociception, pain and emotional suffering; mindful breathing and body scan
2	Automatic pain coping habits; awareness of automatic opioid use; instruction in mindfulness of automatic pilot; mindful breathing
3	Mindful reappraisal as means of coping with negative emotions; mindful breathing
4	Savoring natural rewards; positive emotion regulation; mindful savoring practice
5	Mindfulness of opioid craving; contemplation of negative consequences of opioid use; imaginal opioid cue-exposure; mindful breathing
6	The relationship of the stress response to pain and craving; imaginal stress exposure; mindful breathing; body scan
7	Concepts of thought suppression, aversion, and attachment; exercise in the futility of thought suppression; mindful breathing and acceptance

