- Time until MMT dropout assessed through clinic records (abstracted by the study counselor who will have access to the clinic records). Time until dropout will be calculated from enrollment until last dose of methadone.
- Total days of methadone treatment assessed through clinic records (abstracted by the study counselor who will have access to the clinic records). Number of days will be calculated from enrollment until each follow-up time-point.
- Total days of opioid or any drug use assessed through EMA data and timeline follow-back
- Trajectories of positive and negative affect assessed through Positive and Negative Affect Schedule.
- Drug craving assessed with an adapted version of the Penn Alcohol Rating Scale.
- Pain severity and pain interference assessed with [the Brief Pain Inventory and the Graceley Box scale⁸](#)

Additional secondary outcome and other relevant measures that could mediate or moderate outcomes will be piloted for feasibility of administration. Details of the measures to be piloted are described below.

Ecological Momentary Assessmenet (EMA) data collection (ongoing from baseline to 16 weeks). The EMA will be programmed as a REDCap survey delivered over a password-protected smart phone that will not store any EMA data. REDCap is a secure, HIPPA-compliant, web-based application for building and managing online surveys and databases. The EMA survey approach will involve 1) collecting event-contingent records of lapses when they occur as well as 2) regular random assessments, prompted by random text messages initiated by Twilio, twice daily via smartphones. For event-contingent records, participants will be asked to initiate an entry when an opioid lapse or opioid craving without use occurs, and note how they were feeling and the extent of craving. One random assessment probe will be scheduled between 9 am and 3 pm and one will be scheduled between 3 pm and 9 pm. The random probes will be generated by an algorithm in REDCap and linked to a Twilio phone number. For random assessments, participants will be asked to note how they are feeling, drug use, and whether they completed their homework (if in the intervention group). Research staff will demonstrate to study participants how to use the phones, respond to the prompts, and provide event contingent data. Research staff will observe participants using the phone and practice using the phone with participants until they are capable of using it.

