As we have done in prior studies, a manual of procedures will be developed during the initial start-up period that explicitly describes the specific procedures related to data collection, entry, storage, and quality assurance for both study conditions. Data will be collected by research staff in strict accordance with the study's protocols. All data collection forms will be independently reviewed for quality and consistency by a member of the research team who was not responsible for collecting the source data. The research staff will be trained to avoid omissions in data collection and data entry. Computer entry protocols will be programmed to avoid accidental skipping of question items. We will apply conditional formatting to datasheets to remove the possibility of out of range data. All data on written forms will be entered twice by two separate data entry personnel and compared via a macro we have experience using within Microsoft Excel datasheets other data will be entered directly into a secure Qualtrics databases. Once all data on paper forms is entered, paper forms will be housed at a facility that specializes in the storage of medical/research information. The destruction date of these files will be within 10 years from the termination of the study and will be authorized by the Principal Investigator. Under supervision from [name], the Research Assistant will conduct monthly descriptive summaries on all data to ensure their accuracy. This will not involve completing any statistical comparisons. If problems are noted in data entry (e.g., out of range values, missing values), the Research Assistant and [name] will investigate the root cause, and solutions to rectify the problem will be generated and implemented.

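### The study counselor, one of the roles that may lead the MORE groups, is the only named abstractor of MMT dropout and methadone days, and the plan neither separates the two tasks nor masks the abstraction

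*Combined protocol and SAP*

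**What the plan says.** **Who abstracts.** Section 1.9 B (Study Instruments) names one abstractor for each of the two clinic-record outcomes: "Time until MMT dropout assessed through clinic records (abstracted by the study counselor who will have access to the clinic records" and "Total days of methadone treatment assessed through clinic records (abstracted by the study counselor who will have access to the clinic records". Dropout time runs from enrollment to the last methadone dose. Methadone days are counted from enrollment to each follow-up.

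**Who delivers MORE.** Section 1.3 A has "two-hour group sessions led by a clinic or study counselor". Section 1.6 A is less specific: "The MORE arm will participate in eight, weekly, two-hour group sessions led by a therapist".

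**Rank of the outcomes.** Section 1.3, under endpoints, states: "Preliminary outcome measures to be assessed during this pilot study will be time until opioid lapse and MMT dropout". It continues: "Preliminary secondary outcomes will be: days of methadone medication use". They correspond to hypotheses 2 and 4 in Section 1.1 B. Sections 1.6 B and 1.9 B present them as exploratory; the main objective is feasibility.

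**Who collects the other outcome data.** Research staff collect interviews and drug screens in both arms (Section 1.9 A), and research assistants collect and process specimens (Section 1.8).

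**Checks.** Section 6.1 D says "All data collection forms will be independently reviewed for quality and consistency by a member of the research team", and that this reviewer must not have collected the source data.

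**What is absent.** The available text does not mention blinding or masking of any assessor, and has no rule keeping the MORE leader apart from record abstraction. Sections 4.10 and 4.11, whose headings cover chart and record review, are marked not applicable.

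**The concern.** A person who leads MORE groups necessarily knows who is in MORE. If that person also decides from the chart when each participant last received methadone and how many days they were in treatment, two between-arm comparisons rest on coding by someone who delivers the intervention and knows the allocation. These outcomes come from records rather than self-report, so they could have been the best protected in the study.

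The pilot is not powered for efficacy. However, Section 6.1 B gives it the job of supplying a preliminary effect size for a larger study, and Section 1.1 makes testing the study methods its main goal. An abstraction procedure left open to this overlap could be carried into the planned R33 (N=150, Section 1.3).

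**Working it through.** The plan gives no figure to reproduce. The check sets the relevant statements side by side.

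**1. Is the overlap certain or only permitted?**

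| Who leads MORE | Leader also abstracts? | Masked abstraction provided? |
|---|---|---|
| Study counselor (permitted, Section 1.3 A) | Yes, under Section 1.9 B | No |
| Clinic counselor (permitted, Section 1.3 A) | No | No |
| Therapist (Section 1.6 A, role not further defined) | Cannot be determined | No |

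The overlap is permitted, not established. The lack of masking is common to all three rows.

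**2. Does it cover both arms?** Section 1.9 B does not say so for the abstraction itself. It follows from the between-arm hypotheses and from there being only one named abstractor. This is an inference, and a reasonable one.

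**3. Is there room for judgement in the coding?** A recorded dispensing date is objective. Deciding which dose was the last one before dropout is less so:
- Section 1.9 B gives no gap length and no rule for transfers or censoring.
- Section 1.6 A says take-home doses are taken on days without clinic attendance, and that their timing varies across clinics.
- Section 2.2 says the Lennard Clinic also provides suboxone, so a change of medication would need coding.

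The missing operational rule is a separate gap and would remain under a masked abstractor. Its relevance here is that it leaves discretion to whoever abstracts.

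**4. Do existing checks close the gap?**
- The methadone screen (Section 1.8) is done by research assistants at baseline, 8 and 16 weeks. It corroborates engagement but cannot date a last dose, and it is missing for telephone assessments (Section 1.9 A).
- The second-person review (Section 6.1 D) is independent of the data collector. It is not described as masked or as a comparison with the clinic record.
- Double entry (Section 6.1 D) compares two entries from written forms, so it detects entry errors, not abstraction choices.

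**5. Scale.** Arm sizes are 15 MORE and 16 TAU (Section 1.5).
- One MORE record coded differently: 1/15 = 6.7 percentage points of that arm's dropout proportion.
- Two MORE records: 2/15 = 13.3 points.
- One TAU record: 1/16 = 6.3 points.

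These show how sensitive small arms are. They do not estimate bias, and they concern a proportion while the stated outcome is a time to event.

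**6. Do the progression decisions depend on it?** The milestones in Section 1.1 B are recruitment (75% of the planned sample), attendance (50% at four or more sessions) and follow-up (65% at 8 weeks, 50% at 16 weeks). None uses the abstracted methadone data.

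**The case against.** The strongest reply is that this is a small matter in an unpowered feasibility pilot. The outcomes are exploratory, the last dose is largely a recorded fact, a drug screen run by other staff gives partial corroboration, and a second person reviews the forms. All of that stands, and it limits the weight of the point.

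A reader might go further and infer that the interventionist is the outcome assessor and that the coding would favour MORE. The documents do not support that:
- The study counselor is one of two alternatives in Section 1.3 A, and Section 1.6 A says only that a therapist leads.
- No section says that group leaders learn of missed doses, take-homes or transfers in sessions; the content in Table 3 is mindfulness, reappraisal and savoring. Nor does any section say that TAU participants are known to the counselor only through the chart.
- Extra knowledge of MORE participants could reveal dropouts as easily as hide them, so no direction can be assigned.
- It also cannot be asserted that the Section 6.1 D review ignores the clinic record. The text does not say what the forms are compared with.

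A further fair objection is that moving the coding to research staff does not guarantee masking. Research staff transcribe MORE recordings (Section 1.9 A), and incentive logs link subject ID to payments that include session cards given only to MORE participants (Section 4.8). This stands, and the fix has to allow for it.

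**Conclusion.** The point holds as a gap in role separation and masking, limited to time to MMT dropout and total methadone days. The plan permits an unmasked interventionist to code both, and provides masked abstraction whoever leads the groups in no case. The conclusion assumes that the single named abstractor covers both arms, and that silence on masking means none is planned.

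The size and direction of any bias are not computable from the documents; the 6.7 and 6.3 points per record are illustrations only. Recruitment, attendance and follow-up milestones are untouched. The change is still worth making because it is cheap, follows the plan's own practice of giving other outcome data to research staff, and protects a named preliminary outcome meant to inform the R33.

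**What to change.** In Section 1.9 B, separate access to the clinic record from coding of the outcome:

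1. State that whoever leads MORE does not code MMT dropout or methadone days.
2. Let the study counselor, who already has record access, obtain a dated dispensing record for each participant, labelled by study ID only.
3. Have an existing research staff member who does not deliver MORE code the last-dose date and methadone days for all 31 participants, under one written rule applied identically to both arms. Where feasible, choose someone who does not transcribe MORE sessions or handle session incentives.
4. If step 3 is not feasible, require the second-person review in Section 6.1 D to compare the coded values with the dispensing record, with arm hidden.
5. Report whether the coder was in fact unaware of arm, rather than assuming it.

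The cost is a short added task for existing staff covering 31 records, and record permissions that include them. The availability of a dated dispensing record from each clinic is an assumption to confirm. Randomization, sample size and visits do not change.

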All study participants will partake in a total of three interviews lasting up to 90 minutes and occurring at baseline, 8- and 16- weeks post-baseline in a private room at NBCC or the Lennard Clinic. Each participant will also have a urine or saliva sample collected during each assessment. This is required to verify self-report of drug use. Due to social desirability, it is common for people to not accurately report drug use; therefore, biochemical verification is the gold standard measure of drug use. All attempts to reach participants to schedule follow-up assessments will be tracked. Participants will also complete cognitive testing (for approx. 30-45 minutes) at baseline and 8-weeks and ecological momentary assessments (EMA) conducted via smartphones, which will be provided to each participant by study staff. EMA participation will require the participant to respond to twice-daily prompts in which they will be asked a series of brief questions regarding their current mood and exposure to opioid triggers. Additionally, subjects will be asked to initiate responses when they experience serious craving or relapse to opioid use. Each EMA assessment will last approximately 3-5 minutes.

B. What data points will be collected including long-term follow-up?

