All study participants will participate in three face-to-face assessments at baseline, 8-weeks, and 16-weeks. If participants are unable or unwilling to attend a research appointment at their clinic, a research assistant will conduct a telephone interview. Information will be collected on demographic characteristics, substance use, methadone treatment, opioid craving and withdrawal, physical pain, non-reactivity, negative and positive affect, attentional bias, cognitive and mental health, physical health, and intervention implementation and attitudes. At the baseline and 8-week research visits, participants will complete three cognitive tasks on a computer that assess inhibitory control, implicit (automatic) associations, and the precedence of global features in visual perception. Urine and/or saliva samples will be requested at each assessment for confirmation of self-reported drug use. In addition, participants will partake in daily ecological momentary assessments (EMA) throughout the 16-weeks of study participation that include brief measures of pain intensity, mood, and substance use. Additionally, participants will be asked to initiate communication via smartphone when they either lapse to opioid use or experience serious craving. Self-initiated responses will include information about the circumstances surrounding their craving/lapse. A synopsis of all study instruments are included below (see 1.9B – Study instruments).

C. Define the duration of the study and the length of time each subject will participate in the study.

This pilot study is expected to take one year. Each subject will participate in the study for a total of 16-weeks.

Describe any primary and secondary study or safety endpoints

Feasibility will be assessed according to recruitment, retention and follow-up benchmarks. We will consider recruitment and retention efforts successful if we are able to enroll 75% of our target enrollment (31 participants) within a period of 4 months. Although we expect to recruit 100% of our planned sample by month 7, we set the criterion at 75% because we could adapt strategies for the next study to increase recruitment (including adding more MMT sites), if necessary. Retention will be considered successful if 50% of participants attend at least 4

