1.8 Primary Specimen Collection

A. *What types of specimen will be collected, where, and by whom?*

We will utilize a urine or saliva screen that tests for buprenorphine and methadone (to provide corroboration of MAT engagement and compliance) and additional substances (e.g., benzodiazepines, barbiturates, cocaine, marijuana, methamphetamine, morphine, oxycodone, phencyclidine and amphetamine). These specimens will be collected by study research assistants at baseline and each follow-up time point (8-weeks and 16-weeks).

Biochemical verification of self-report opioid relapse and other drug use is the gold standard measurement of drug use and, without biochemical verification, self-reported drug use as an outcome variable will be questioned by the scientific community.

B. *How will the specimens be transported and by whom?*

The sample will be collected and results read at the time of sample collection. The sample will be disposed as soon as results are read (typically within 10 minutes of sample collection) and recorded. The sample will not be transported. Samples will be collected and read in a private area where others will not be able to see or hear the results.

C. *Who will process the specimens?*

Research assistants will process the sample.

D. *How long will the specimens be kept?*

The sample will be disposed of immediately after results are read and recorded.

E. *How will the specimens be destroyed upon study completion?*

Samples will be flushed down the toilet (urine test) or disposed of in the trash (saliva test).

F. *If specimens will be banked for future use, what will be the process for providing investigators with access to the bank and how will this be tracked?*

N/A

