Data will be received by the REDCAP system. Data access between the REDCap database and the web server is encrypted and restricted to a monitored port. All REDCap data, which is displayed or captured by the user interface, is encrypted for security. Within REDCap all data transactions including inserts, updates, deletions, import/export and reporting are logged. The EMA system in this study deployed via REDCap will reside in a HIPAA compliant protected space. The REDCap production and development servers use encrypted drives. Physical hardware will be secured in a locked facility.

The data will only be accessible to study investigators and staff. The data will be processed by an already developed REDCap program that formats the data as a "long file" with one row per time point per individual participant. The investigators will employ linear mixed models to test the effects of MORE vs. the control condition on substance use, craving, pain, and other study variables. The treatment X time interaction will be the main fixed effect of interest. Models will include a random intercept, as well as a random slope if warranted by model fit statistics. Auto-correlation between repeated measures will be modeled as a first-order autoregressive function. We will also compute within-group linear mixed models examining mindfulness practice duration as a predictor of clinical outcomes.

Substance use history (Baseline). We will use the PhenX Toolkit-Substance Abuse and Addictions Core Tier 1 Collection² to gather self-report information on lifetime use of opiates, alcohol, tobacco and substances, and past-30 day use of all substances.

Current substance use (Baseline, 8 weeks, and 16 weeks). We will utilize a urine screen that tests for buprenorphine and methadone (to provide corroboration of MAT engagement and compliance) and additional

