substances (benzodiazepines, barbiturates, cocaine, marijuana, methamphetamine, morphine, oxycodone, phenyclidine and amphetamine). At each research visit we will conduct a timeline follow-back³ with each participant to account for missing EMA drug use data. The timeline follow-back is a reliable and valid measure where participants are asked to recall and record events (e.g., drug use) within a specified time period on a calendar. We will combine self-report of opioid relapse and other drug use with biochemical measures because it is the gold standard, and without biochemical verification, self-reported drug use as an outcome variable will be questioned by the scientific community. If a biochemical measure is negative, but the participant reports drug use, the participant will be coded as using drugs since the biochemical measure will only capture a specific time point. However, if the participant self-reports drug abstinence, but the biochemical measure is positive for drug use (the more likely scenario) the participant will be coded as having used drugs.

Craving (Baseline, 8 weeks, and 16 weeks). Opioid and other drug craving will be assessed with an adapted version of the Penn Alcohol Craving Scale (PACS)⁴ and the Craving Suppression Scale. The PACS is a valid, reliable, and internally consistent measure that consists of five self-report items that have been found to predict relapse. The items assess the intensity, frequency, ability to resist, and duration of craving. Originally developed to assess alcohol craving, it has been adapted and used to measure craving for various substances, including opioids,⁵ and adapted versions have been used in trials of mindfulness-based interventions for substance use.⁶ The Craving Suppression Scale is a 17 –item measure that assesses how individuals cope with craving

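### The drug screen names morphine and oxycodone as its only non-treatment opioids and leaves the specimen type unsettled, so denied use of an unlisted opioid would be coded as abstinence

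*Combined protocol and SAP*

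**What the plan says.** **Panel.** Section 1.9 B (Current substance use) tests for buprenorphine, methadone and additional "substances (benzodiazepines, barbiturates, cocaine, marijuana, methamphetamine, morphine, oxycodone, phenyclidine and amphetamine". Read alone, this is a closed list. Section 1.8 A gives the same analytes only as examples: "additional substances (e.g., benzodiazepines, barbiturates, cocaine, marijuana, methamphetamine, morphine, oxycodone, phencyclidine and amphetamine". The treatment drugs have their own purpose, since the device "tests for buprenorphine and methadone (to provide corroboration of MAT engagement and compliance". Neither list names fentanyl.

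**Role of the screen.** Section 1.9 B states: "We will combine self-report of opioid relapse and other drug use with biochemical measures because it is the gold standard". Its coding rule has two parts. Reported use counts as use even if the screen is negative, because a screen reflects only one time point. Reported abstinence with a positive screen also counts as use, and the plan expects this to be the commoner disagreement. Section 1.3 A adds that inaccurate reporting of drug use is common.

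**Specimen.** The sections differ:
- Section 1.3 A: "Each participant will also have a urine or saliva sample collected during each assessment".
- Section 1.3 B: "Urine and/or saliva samples will be requested at each assessment for confirmation of self-reported drug use".
- Section 1.8 A: "We will utilize a urine or saliva screen that tests for buprenorphine and methadone".
- Section 1.9 B: "We will utilize a urine screen that tests for buprenorphine and methadone".

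No section says how the type is chosen or whether it stays the same across visits. Under section 1.8, samples are read on the spot, discarded at once and not banked.

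**The concern.** The screen protects the drug-use outcomes against one failure: a participant who used and says otherwise. It can do so only for substances it detects. If a lapse involves an opioid outside the panel, the safeguard is absent for exactly the participants who need it. The plan acknowledges the time-point limit of a negative result but not the coverage limit.

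Section 6.1 B says the pilot is to provide a preliminary effect size for a larger study. Missed use would lower the recorded use in both arms and could shrink an absolute difference between them. Mixing specimen types could also make detection vary between visits or arms. Because specimens are discarded, a missing assay cannot be run later, so the panel has to be settled before collection.

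**Working it through.** The plan states no assay sensitivity or lapse rate by drug, so there is no figure to reproduce. The check is mainly one of text and logic.

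**1. Can an unlisted opioid be presumed detected?** The panel lists methadone, buprenorphine, morphine and oxycodone separately. Section 4.2 D requires at least 3 months in methadone treatment. A morphine test that reacted to any opioid would be positive in every participant taking methadone and would be useless here. The design therefore presupposes drug-specific tests. Whether a particular device detects fentanyl is not stated in the documents. The point is that the plan does not show that it does.

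**2. The coding rule, case by case.**

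| Self-report | Screen | Coded as |
|---|---|---|
| Use | Positive or negative | Use |
| Abstinent | Positive | Use |
| Abstinent | Negative | Abstinent (implied; no disagreement to resolve) |

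A participant who denies use, took only an undetected opioid and is negative for everything else falls in the last row. One who reports use falls in the first row and is coded correctly.

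**3. Illustrative size (assumptions, not document figures).** Let f be the share of lapsers whose only detectable-in-principle drug is an unlisted opioid, and u the share of those who deny it. The share of lapsers coded abstinent by this route is f × u.
- Low: 0.10 × 0.25 = 0.025.
- High: 0.75 × 0.75 = 0.5625.

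Section 1.2 gives 50% relapse within six months among patients retained in methadone treatment. Under a constant hazard, the 16-week rate is 1 − 0.5^(16/26) = 0.347. The number affected among 31 is then:
- Low: 31 × 0.347 × 0.025 = 0.3.
- High: 31 × 0.347 × 0.5625 = 6.1.

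With a 50% lapse rate over the 16 weeks, the range is 0.4 to 8.7. These ranges are wide because f and u are unknown.

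**4. What an added assay could recover.** Less than step 3 suggests. There are only two follow-up screens in 16 × 7 = 112 days. With an assumed detection window of 3 days, they cover 2 × 3 / 112 = 5.4% of the period; with 1 day, 1.8%. A single isolated lapse would usually be missed whatever the panel. For a once-weekly user, the chance of a positive at any one screen is 3/7 = 43% or 1/7 = 14%, so the gain is mainly in repeated use.

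**5. Effect on the arm comparison.** Suppose a fraction s of true users is detected in both arms, with no false positives. The risk difference becomes s × (p0 − p1), while the risk ratio s·p1 / s·p0 is unchanged. For example, take assumed rates of 0.50 and 0.35 and s = 0.75. The recorded rates are 0.375 and 0.2625, the difference falls from 0.15 to 0.1125, and the ratio stays at 0.70.

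**6. Specimen type.** Sections 1.3 and 1.8 allow a change from urine to saliva between visits; section 1.9 B does not. The documents give no detection characteristics for either, so no size follows.

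**The case against.** The strongest reply is that little depends on the screen. Time to first lapse and days of use are sourced from EMA and the timeline follow-back (section 1.9 B), and reported use already overrides a negative. No feasibility milestone uses a screen result, drug use is exploratory, and section 6.1 disclaims power. The illustrative in section 1.8 A also leaves open whether the device tests for more than the list shows. All of this stands, and it limits the point to unreported use in exploratory outcomes.

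It does not remove the point. Unreported use is why the plan has a screen, and section 1.9 B says biochemical results will be combined with self-report of relapse. If the device has a wider panel, section 1.9 B still needs correcting.

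A reader might infer more than the documents support:
- *That the device tests only morphine and oxycodone.* The supportable statement is that these are the only non-treatment opioids named.
- *That the plan takes a negative as proof of abstinence.* The coding rule shows otherwise.
- *That mixed specimens distort change from baseline in screen results, or that the type is chosen after randomisation.* No such change analysis is planned, and the timing of the choice is not stated.
- *That any arm difference must shrink.* Step 5 shows that a risk ratio need not.

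**Conclusion.** The point holds in limited form. As written, the panel does not show coverage of opioids other than morphine, oxycodone and the treatment drugs. A participant who denies use of one outside it, and is otherwise negative, is coded abstinent. The specimen type is inconsistent across four places, so detection may vary between visits or arms.

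Only the direction is established: under-detection of unreported opioid use, with absolute differences reduced if detection is equal in the two arms. The size cannot be derived from the documents. The range of about 0.3 to 8.7 participants of 31 rests entirely on assumed f and u and on a lapse rate carried over from the background section, and an added assay would recover only part of it. Recruitment, retention and follow-up benchmarks are not affected. The change is still worth making, because it is cheap and the omission cannot be repaired once specimens are discarded.

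**What to change.** 1. In sections 1.8 A and 1.9 B, state one complete panel, identical in both places and not introduced as examples. Include a fentanyl assay run on the same specimen, and count a positive as opioid use under the existing coding rule.
2. Reconcile sections 1.3 A, 1.3 B, 1.8 A and 1.9 B to urine at baseline, 8 and 16 weeks, as section 1.9 B already has it, with saliva only when urine cannot be provided.
3. Record the specimen type at each visit and tabulate it by arm.
4. Report a negative as negative for the listed analytes at that time, so that the coverage limit stands beside the time-point limit the plan already states.

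No rule confining between-visit comparisons to one specimen type is needed, since the plan proposes no such comparison.

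Cost: a slightly dearer device or one extra strip for at most 31 × 3 = 93 screens, and fewer where an assessment is done by telephone and the screen is missing. No added visit, specimen or staff.
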